5.6.4 Vital Signs

Summary statistics for vital signs parameters (diastolic and systolic blood pressure, pulse, and temperature), and weight and changes from baseline will be presented by time point.

Subject data listings will be provided.

5.6.5 Electrocardiograms

The results of ECG assessments performed at each visit will be evaluated. Summary statistics for ECG parameters (Heart Rate, RR, PR, QRS, QT, and QTcF) and changes from baseline will be presented by time point.

Shift tables will present changes from baseline in ECG interpretation (categorized as normal; abnormal, not clinically significant; and abnormal, clinically significant) to each visit.

In addition, the number (percentage) of subjects who met below criteria at least once in QTcF will be presented:

Absolute QTcF interval prolongation:

- QTcF interval >450 ms
- QTcF interval >480 ms
- QTcF interval >500 ms

Change from baseline in QTcF interval:

- QTcF interval increases from baseline >30 ms

- QTcF interval increases from baseline >60 ms

Subject data listings will be provided.

5.6.6 Other Safety Analyses

LVEF

LVEF and change from baseline will be summarized at each time point.

The result of LVEF will be categorized into hyperdynamic (>70 %), normal ($\geq 50 - 70\%$), mild dysfunction ($\geq 40 - 50\%$), moderate dysfunction ($\geq 30 - 40\%$), Severe dysfunction (<30%), and shift from baseline to worst postbaseline will be reported using shift table with below levels.

- Hyperdynamic/Normal
- Mild Dysfunction
- Moderate Dysfunction
- Severe Dysfunction

Subject data listings will be provided.

ECOG PS

ECOG PS will be summarized by scale at each visit and by highest postbaseline scale.

Subject data listings will be provided.

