### 9.3.1 Inclusion Criteria

1. Subjects must meet all of the following criteria to be included in this study: Voluntary agreement to provide written informed consent of this study
2. Willing and able to comply with all aspects of the protocol after being fully informed of the content
3. Males or females aged  $\geq 20$  years at the time of informed consent
4. Histological or cytological confirmation of RCC
5. Subjects must have confirmed diagnosis of unresectable advanced and/or metastatic RCC
6. Disease progression following VEGF targeted therapy
7. Eastern Cooperative Oncology Group (ECOG) Performance Status (PS) of 0 to 1
8. Adequately controlled blood pressure with or without the use of antihypertensive agents (defined as BP  $\leq 150/90$  mmHg at screening and no change in antihypertensive therapy within 1 week prior to the Cycle 1 Day 1
9. Subjects with adequate function of major organs:
  - a. Hemoglobin  $\geq 9.0$  g/dL
  - b. Neutrophil count  $\geq 1.5 \times 10^3 /\mu\text{L}$
  - c. Platelets  $\geq 10 \times 10^4 /\mu\text{L}$
  - d. Total bilirubin  $\leq 1.5 \times$  upper limit of normal specified by the testing laboratory (ULN)
  - e. Alkaline phosphatase (ALP), AST and ALT  $\leq 3.0 \times$  ULN ( $\leq 5.0 \times$  ULN for patients with the liver metastasis)
  - f. Creatinine clearance  $\geq 40$  mL/min calculated per the Cockcroft and Gault formula  
Male:  $(140 - \text{age}) \times \text{weight (kg)} \div 72 \times \text{Serum creatinine (mg/dL)}$   
Female:  $0.85 \times (140 - \text{age}) \times \text{weight (kg)} \div 72 \times \text{Serum creatinine (mg/dL)}$

10. Adequate blood coagulation function, defined as international normalized ratio (INR)  $\leq 1.5$
11. Survival expectation of 3 months or longer after study enrollment
12. Washout period required from the end of prior treatment to the start of study drug administration will be as follows:
  - a. Anticancer therapies:
    - Other investigational drug or antibody therapy:  $\geq 4$  weeks
    - Chemotherapy (except small-molecule targeted therapy), surgical therapy, radiation therapy:  $\geq 3$  weeks
    - Endocrine therapy, immunotherapy, small-molecule targeted therapy:  $\geq 2$  weeks
  - b. Supportive therapies:

Blood transfusion, blood preparations, hematopoietic growth factors including G-CSF preparations:  $\geq 2$  weeks

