5.2.4 Demographic and Other Baseline Characteristics

Demographic and other baseline characteristics for the Safety Analysis Set and Pharmacokinetic Analysis Set will be summarized using summary statistics. Continuous demographic and baseline variables include age, height, and weight; categorical variables include sex, race, ethnicity, ECOG PS, NYHA, diagnostic information (metastatic sites, number of metastatic site, histological type, time since RCC diagnosis to first dose of study treatment, TNM categories and stage), prior therapy (nephrectomy [yes or no], radiotherapy [yes or no], sites of radiotherapy, anti-cancer medication [yes or no], type of anti-cancer medication [axitinib, everolimus, and so on.], number of VEGF targeted therapy [1 regimen, 2 regimens, 3 regimens] and other therapies [yes or no]), treatment duration and reason for discontinuation of last anti-cancer medication, hypertension (yes or no), and creatinine clearance (\geq LLN, $<$ LLN and ≥ 60 mL/min, and 60-40 mL/min).

The categories for metastatic site, site of previous radiotherapy, type of prior anti-cancer medication depend on actual data.

Subject data listings will be provided.

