5.6.3 Laboratory Values

Laboratory results will be summarized using Système International (SI) units. For all quantitative parameters listed in protocol Section 9.5.1.3.5, the actual value and the change from baseline to each postbaseline visit, the highest and lowest postbaseline values will be summarized by visit using summary statistics. Qualitative parameters will be summarized by number and percentage of subjects, and changes from baseline to each postbaseline visit and the highest postbaseline result will be reported using shift tables. Percentages will be based on the number of subjects with both nonmissing baseline and relevant postbaseline results.

Laboratory test results will be assigned a low/normal/high (LNH) classification according to whether the value is below (L), within (N), or above (H) the laboratory parameter's reference range. The result of LNH classification will be provided in a subject data listing.

Laboratory parameters will be graded by CTCAE ver. 4.03 in "[13 APPENDICES](#)". Changes from CTCAE grade at baseline to each postbaseline visit and worst postbaseline will be reported using shift tables. As for thyroid stimulation hormone, values at baseline and worst postbaseline will be categorized into ≤ 0.5 , $>0.5 - 2.0$, $>2.0 - 5.5$, >5.5 ($\mu\text{IU/mL}$) and summarized.

CTCAE ver. 4.03 will be used to identify subjects with Treatment-emergent markedly abnormal laboratory value (TEMAV). TEMAV is defined as a value with postbaseline value with a grade increase from baseline by 2 or higher. (i.e., Increasing grade 0 to 2 or higher, grade 1 to 3 or higher, grade 2 to 4 or 5.) For phosphate, TEMAV is defined as a value with postbaseline value with a grade increase from baseline by 3 or higher. The number (percentage) of subjects with TEMAV (markedly abnormal high/low) will be summarized by visit. When displaying the incidence of TEMAVs, each subject will be counted once in the laboratory parameter high and in the laboratory parameter low categories, as applicable.

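### ECOG PS is never compared with baseline, so the number of subjects who worsened cannot be read from the planned tables; the TSH category summary leaves crossing and the direction of worst unstated

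*SAP*

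**What the plan says.** **ECOG PS.** SAP 5.6.6 gives it one sentence of analysis: "ECOG PS will be summarized by scale at each visit and by highest postbaseline scale". Protocol 9.7.1.9 words it the same way. The only other output there is individual data: "Subject data listings will be provided". Entry status appears separately in the baseline table of SAP 5.2.4, where "categorical variables include sex, race, ethnicity, ECOG PS, NYHA". Protocol 9.3.1, criterion 7, admits "Eastern Cooperative Oncology Group (ECOG) Performance Status (PS) of 0 to 1". SAP 5.1.1 names ECOG PS among the primary safety endpoints.

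**Comparators.** For LVEF, directly above ECOG PS in SAP 5.6.6, the "shift from baseline to worst postbaseline will be reported using shift table with below levels". For graded laboratory values, SAP 5.6.3 says: "Changes from CTCAE grade at baseline to each postbaseline visit and worst postbaseline will be reported using shift tables". SAP 5.6.5 also plans shift tables for ECG interpretation.

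**TSH.** SAP 5.6.3 says: "As for thyroid stimulation hormone, values at baseline and worst postbaseline will be categorized into" four bands (≤0.5, >0.5–2.0, >2.0–5.5 and >5.5 µIU/mL), which are then summarised. For quantitative laboratory parameters in general, "the actual value and the change from baseline to each postbaseline visit, the highest and lowest postbaseline values will be summarized by visit".

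**The concern.** A safety summary of performance status should say how many subjects got worse on the combination. A count of highest values answers a different question, namely how many subjects were ever at each level. With entry allowed at two levels, the PS 1 row contains both stable subjects and deteriorated ones.

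ECOG PS is the only variable in the primary safety list with no planned comparison with baseline. Adverse events are defined relative to the pretreatment state (SAP 8.1). Laboratory values, vital signs, weight, ECG and LVEF all have change from baseline, shift tables or both.

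For TSH there are two gaps in the text. It does not say whether the baseline and worst bands form a cross-table or two separate columns. It also does not say which direction counts as worst, although both end bands are open. A subject in the lowest band at one visit and the highest band at another has no determinate worst category, and two programmers could report different ones. The topic matters here: hypothyroidism is among the events seen in at least 20% of the combination arm of Study 205 (Protocol 7.3.2.2), and Protocol 7.4 asks for TSH monitoring.

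**Working it through.** The plan states no figure to reproduce. The check asks whether the planned counts determine the number of subjects who worsened. All counts below are assumptions chosen for illustration, because the documents contain no such data. The totals of 6 and 12 come from SAP 4.

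**ECOG PS.** Let b0 be the number entering at PS 0. Let h0, h1 and h2 be the numbers whose highest postbaseline PS is 0, 1, and 2 or more. Let x be the number who moved from 0 to 1. Everyone in h2 has worsened, because entry is limited to 0–1. So

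number worsened = h2 + x.

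The tables give h2 but not x. The possible values of x are:

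- nobody improves (so h0 contains only PS 0 entrants): from max(0, b0 − h0 − h2) to min(h1, b0 − h0);
- improvement possible (a PS 1 entrant has every postbaseline value at 0): from max(0, b0 − h0 − h2) to min(b0, h1).

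| Entry PS 0/1 | Highest 0/1/≥2 | x, nobody improves | Worsened | x, improvement possible | Worsened |
|---|---|---|---|---|---|
| 6/6 | 3/5/4 | 0–3 | 4–7 of 12 (33–58%) | 0–5 | 4–9 (33–75%) |
| 6/6 | 4/6/2 | 0–2 | 2–4 of 12 | 0–6 | 2–8 |
| 6/6 | 6/6/0 | 0 | 0 of 12 | 0–6 | 0–6 |
| 3/3 | 2/2/2 | 0–1 | 2–3 of 6 | 0–2 | 2–4 |
| 3/3 | 2/3/1 | 0–1 | 1–2 of 6 | 0–3 | 1–4 |

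First row, nobody improving: the lower limit is max(0, 6 − 3 − 4) = 0 and the upper limit is min(5, 6 − 3) = 3, so 4 + 0 to 4 + 3. The by-visit counts do not settle x in general, since they are also margins. If there is only one postbaseline assessment, they are the same counts.

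In a shift table x is a cell, so each range becomes one number.

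**TSH, only if the bands are not crossed.** With N subjects, B above 5.5 at baseline and W above 5.5 at worst, the number newly above 5.5 lies between max(0, W − B) and min(W, N − B). For N = 12, B = 3, W = 6 this is 3 to 6. For N = 6, B = 1, W = 3 it is 2 to 3. If the bands are crossed, the number is exact.

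SAP 13.1 has no TSH row, so the CTCAE-based shift tables do not reach TSH. SAP 8.1 has a furthest-from-normal rule, but only for observations equally close to one target visit day. It does not define the worst postbaseline value.

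**The case against.** The strongest reply is that little is lost. Because entry is limited to PS 0–1, any highest PS of 2 or more is new deterioration and can be read directly. Baseline PS is tabulated, and subject listings cover 6 to 12 subjects per dose group, so a reader can reconstruct every shift. The upper ends of the wider ranges need PS 1 entrants to improve to 0 throughout while others worsen: reaching 9 of 12 takes at least two of them. No judgement criterion or statistical comparison rests on these tables. All of this stands, and it makes the point minor. It does not remove it: the SAP plans shift tables for LVEF and ECG interpretation with the same few subjects and the same listings.

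On TSH, a reader might infer that the categories are definitely not crossed. The text does not support that. The sentence names baseline and worst postbaseline together, directly after one on shift tables. It neither states nor excludes crossing, and the table shells are a separate document (SAP 11). Nor is either direction wholly lost. If TSH is treated as a quantitative parameter (it is in Protocol Table 3), its change from baseline and its highest and lowest values are summarised. New thyroid events also appear as TEAEs. What remains is that the categorical display is underspecified and worst has no direction.

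A reader might also argue that prior VEGF-targeted therapy makes abnormal TSH at entry likely. The documents give no support for that link, and the point does not need it.

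**Conclusion.** For ECOG PS the point holds. The specified tables give only margins, 0-to-1 deterioration cannot be separated from PS 1 at entry, and the total who worsened is generally not identifiable from them. In the assumed examples with nobody improving, the uncertainty is at most 3 of 12 subjects (4 to 7) or 1 of 6. It would be wrong to conclude that no deterioration is visible: PS 2 or worse is, provided that no subject is enrolled outside the PS criterion.

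For TSH the supported finding is narrower: crossing is unstated, and worst is undefined on a scale open at both ends.

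This is a minor reporting improvement with no bearing on the DLT analysis or the sample size.

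**What to change.** - **SAP 5.6.6:** replace the highest-postbaseline count with a shift table of baseline PS by highest postbaseline PS, and report n (%) of subjects with any increase, among those with a baseline and at least one postbaseline value. The column totals keep the count now planned, so nothing is lost.
- **SAP 5.6.3:** present TSH as baseline category by highest postbaseline category and, separately, baseline category by lowest postbaseline category, in place of one undirected worst value.
- **SAP 7:** record both as additions to the protocol analyses.

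The cost is a few lines of SAP text and three small tables, in a format the SAP already uses and from data already collected.

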5.7 Other Analyses

Not applicable.

5.8 Exploratory Analyses

No exploratory analyses are planned for this study.

6 INTERIM ANALYSES

No interim analysis is planned for this study.

7 CHANGES IN THE PLANNED ANALYSES

The below analyses were added from protocol to establish analyses for CSR:

- The items of demographic and other baseline characteristics were detailed.
- The analysis for dose interruption and dose reduction were added.
- The analysis for PFS and calculation of DOR were added.
- A waterfall plot for the percent changes from baseline in the sum of the diameters of target lesions was replaced to spaghetti plot.
- An overview table of TEAEs was added.
- The analysis for TEAEs and treatment-related TEAEs were enhanced.
- The shift table of laboratory values based on CTCAE grades was added.
- The analysis for TEMAV and its definition were added.
- The categorical analysis for LVEF was added.

The below analysis was deleted from protocol

- The analysis for time course change in tumor marker was deleted as the amount of data is not sufficient.

8 DEFINITIONS AND CONVENTIONS FOR DATA HANDLING

The data will be handled as follows. The sponsor will determine how to handle all data prior to data base lock.

8.1 General Data Handling

Baseline

Baseline is defined as the last non-missing value observed prior to the first dose of study treatment for a given parameter.

Change from Baseline, Percent Change from Baseline

Change from baseline is defined as post-baseline value minus baseline value.

Percent change from baseline is defined as follows:

$$\% \text{ Change from baseline} = (\text{Change from baseline}/\text{Baseline}) * 100\%$$

For any Baseline value of 0, the subject's corresponding percent change from baseline will not be included in the summary statistics table.

Handling of Missing data

No imputation will be performed for missing data.

Handling of data not within specified periods or within the follow-up period

All the safety parameters will be used for summary statistic tabulation, except when it is irrelevant like the situation that tests scheduled to be conducted before administration of the investigational drug are actually conducted after its administration. Data obtained not within the time window specified in the protocol will be handled as missing data for summary tables by visit. Data obtained after the follow-up assessment, which is scheduled for 30 days after the last administration of study treatment, will not be used for analysis.

Handling of multiple data

In the case of multiple observations within the specified time window of a specific analysis visit, the observation closest in date and time to the target visit day will be used in summary tables by visit. If two or more observations have the same distance to the target visit day, the one that has the highest CTCAE grade or is furthest away from the normal range will be used for safety analyses. If there are still multiple observations, the handling will be considered individually.

Handling of below lower quantification values in laboratory results

In the cases of laboratory result contains below lower quantification (BLQ) value, it will be replaced to the lower limit of quantification (LLOQ) for summarizing tables.

Calculation of creatinine clearance

To calculate a creatinine clearance (mL/min), the Cockcroft & Gault formula will be used.

Males: $((140 - \text{age (years)}) \times \text{weight(kg)}) / (\text{Creatinine (serum:mg/dL)} \times 72)$

Females: $((140 - \text{age (years)}) \times \text{weight(kg)} \times 0.85) / (\text{Creatinine (serum:mg/dL)} \times 72)$

Treatment-emergent adverse event

A TEAE is defined as an AE that emerged during treatment, having been absent at pretreatment or

- Reemerged during treatment, having been present at pretreatment but stopped before treatment, or
- Worsened in severity during treatment relative to the pretreatment state, when the AE was continuous.

All the adverse events will be considered as TEAE if the AE onset date was on or after the first dose of lenvatinib up to 30 days after last dose of lenvatinib.

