### 9.1.1.2 Follow-up Period

Follow-up Period will include discontinuation assessments and off-treatment visit. Subject will discontinue study treatment if he/she qualifies for any of the criteria listed in Section 9.3.3.1. The discontinuation assessments will occur within 7 days and the off-treatment assessments on 30 days (+ 7 days) after the final dose of study treatment.

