#### **ADVERSE EVENTS AND OTHER EVENTS OF INTEREST**

An adverse event is any untoward medical occurrence in a subject or clinical investigation subject administered an investigational product. An AE does not necessarily have a causal relationship with the study drug. For this study, the study drug is lenvatinib.

The criteria for identifying adverse events are:

- Any unfavorable and unintended sign (including an abnormal laboratory finding), symptom, or disease temporally associated with the use of an investigational product, whether or not considered related to the investigational product. If a diagnosis was made based solely on the sign and symptom, the identified medical condition or disease will be considered as AE.
- Any new disease or exacerbation of an existing disease. However, worsening of the primary disease should be captured under efficacy assessments as disease progression rather than as an AE
- Any deterioration in nonprotocol-required measurements of a laboratory value or other clinical test (e.g., ECG or x-ray) that results in symptoms.
- Any deterioration in nonprotocol-required measurements of a laboratory value or other clinical test (e.g., ECG or x-ray) that results in a change in treatment or discontinuation from study drug
- Recurrence of an intermittent medical condition (e.g., headache) not present at baseline
- An abnormal laboratory test result should be considered an AE if the identified laboratory abnormality leads to any type of intervention, whether prescribed in the protocol or not

All AEs encountered during the clinical study will be reported on the CRF. All AEs, regardless of relationship to study drug or procedure, should be collected beginning from the time the subject signs the study consent through the last visit. Subjects may receive other anti-cancer treatment within 30 days after the final administration of study drug if his/her cancer conditions necessitate. In this case, off-treatment observation must be conducted before initiation of other anti-cancer treatment. For SAEs, all events occurred until 30 days

after the subject's last dose will be collected. If subject was withdrawn prior to and during screening evaluations due to findings meeting the definition of an AE, its severity will be recorded on the Adverse Events CRF.

All laboratory abnormalities meeting the criteria to qualify as an AE should be recorded on the CRF.

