Abnormal laboratory values should not be listed as separate AEs if they are considered to be part of the clinical syndrome that is being reported as an AE. It is the responsibility of the investigator to review all laboratory findings in all subjects and determine if they constitute an AE. Medical and scientific judgment should be exercised in deciding whether an isolated laboratory abnormality should be classified as an adverse event.

A laboratory result should be considered by the investigators to be an AE regardless of the presence of an abnormality laboratory test if it:

- Results in the withdrawal of study drug
- Results in withholding of study drug pending some investigational outcome
- Results in an intervention, based on medical evaluation (e.g., potassium supplement for hypokalemia)
- Results in any out of range laboratory value that in the investigator's judgment fulfills the definitions of an AE with regard to the subject's medical profile
- Increases in severity compared to baseline by  $\geq 2$  CTCAE v4.03 grades, with the exception of lymphocytes, albumin, cholesterol, glucose. For these tests, a change of  $\geq 2$  grades will be evaluated by the investigator to determine if they are of clinical significance and, if so, will be considered an adverse event.

Abnormal ECG (QTc) results, if not otherwise considered part of a clinical symptom that is being reported as an AE, should be considered an AE if the QTc interval (Friderica formula) is  $> 450$  ms and there is an increase of  $> 60$  ms from baseline. Any ECG abnormality that the investigator considers as an AE should be reported as such.

All AEs must be followed until resolution or for 30 days after the subject's last dose, whichever comes first. Serious adverse events will be followed until the event resolves or the event or sequelae stabilize.

**Every effort must be made by the investigator to categorize each AE according to its severity and its relationship to the study treatment.**

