### 9.5.4 Reporting of Serious Adverse Events, Pregnancy, and Events Associated with Special Situations

#### 9.5.4.1 Reporting of Serious Adverse Events

All SAEs, irrespective of relationship to study treatment, must be reported on a completed SAE form by email, fax, or spoken communication as soon as possible, but no later than one business day from the date the investigator becomes aware of the event.

Deaths and life-threatening events should be reported by telephone immediately but no later than one business day. Other SAEs must be reported to the sponsor on a completed SAE form no later than 5 business days.

Serious adverse events, regardless of causality assessment, must be collected through the termination visit and for 30 days following study drug discontinuation, whichever is longer. All SAEs must be followed to resolution, or if resolution is unlikely, to stabilization.

Any SAE judged by the investigator to be related to the study treatment (and/or protocol-specified procedure) should be reported to the sponsor regardless of the length of time that has passed since study completion.

The detailed contact information for reporting of SAEs is provided in Appendix 3.

It is very important that the SAE report form be filled out as completely as possible at the time of the initial report. This includes the investigator's assessment of causality.

Any follow-up information received on SAEs should be forwarded within 1 business day of its receipt. If the follow-up information changes the investigator's assessment of causality, this should also be noted on the follow-up SAE form.

Preliminary SAE reports should be followed as soon as possible by detailed descriptions including copies of hospital case reports, autopsy reports, and other documents requested by the sponsor.

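### SAP 8.1 gives two opposite instructions for SAEs that start within 30 days of the last dose but after an off-treatment visit brought forward for other anticancer therapy

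*SAP*

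**What the plan says.** **The cut-off.** SAP 8.1, at the end of the paragraph on data outside specified periods, states: "Data obtained after the follow-up assessment, which is scheduled for 30 days after the last administration of study treatment, will not be used for analysis". It makes no exception for SAEs or for a visit held early.

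**The visit.** Protocol 9.1.1.2 places "the off-treatment assessments on 30 days (+ 7 days) after the final dose of study treatment"; SAP 3.2.4 gives the same timing. The adverse event text of protocol 9.5.1.3 then adds a case in which the visit moves: "Subjects may receive other anti-cancer treatment within 30 days after the final administration of study drug if his/her cancer conditions necessitate". When that happens, the "off-treatment observation must be conducted before initiation of other anti-cancer treatment". Protocol 9.5.1.7 repeats the rule. No earliest day is set.

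**Collection of SAEs.** Straight after the early-visit rule, protocol 9.5.1.3 requires SAEs up to 30 days after the last dose. Protocol 9.5.4.1 sets the end of collection at the later of the termination visit and 30 days after stopping study drug.

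**The TEAE rule.** Further on in SAP 8.1, an AE is treatment-emergent if its onset is "on or after the first dose of lenvatinib up to 30 days after last dose of lenvatinib". The visit date plays no part. SAP 5.6.2 puts TEAEs and treatment-emergent SAEs into the summary tables, and lists all AEs and all SAEs by subject.

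**The concern.** The cut-off is worded by an event, the follow-up assessment, and takes for granted that this event falls on Day 30. For a subject who moves quickly to another anticancer therapy it does not. An SAE after the early visit but before Day 30 must be collected and meets the TEAE definition, yet the cut-off sentence tells the programmer not to analyse it.

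Adverse events are part of the primary endpoint (protocol 9.7.1.1, SAP 5.1.1). The visit is brought forward because the subject's cancer calls for other treatment, so the subjects exposed to the conflict are selected by their disease course. If the literal cut-off were applied, the SAE count in those subjects could only stay the same or fall.

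**Working it through.** The plan states no figure to reproduce, and the sample size has no statistical basis (SAP 4). The check sets the rules side by side and then sizes one misclassified subject.

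**Step 1. The windows after the last dose.** Let *d* be the day of the off-treatment visit, counted from the last dose.

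| Rule | Source | Ends at |
|---|---|---|
| SAE collection | Protocol 9.5.1.3 | Day 30 |
| SAE collection | Protocol 9.5.4.1 | Later of termination visit and Day 30 |
| TEAE definition | SAP 8.1 | Day 30 |
| Data usable for analysis, read literally | SAP 8.1 | Day *d* |

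The TEAE rule counts from the last lenvatinib dose, the cut-off from the last study treatment. Protocol 9.3.3.1 stops everolimus when lenvatinib is withdrawn, so I treat the two dates as the same.

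**Step 2. Days in conflict.** These number 30 − *d* when *d* is below 30, and none otherwise. The documents give no value for *d*. Over an assumed range of 1 to 29:

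- *d* = 1: 30 − 1 = 29 days
- *d* = 29: 30 − 29 = 1 day
- *d* = 30 to 37 (on schedule): 0 days within the 30-day window

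**Step 3. An event in the gap.** Take an SAE with onset on Day 15 and a visit before Day 15. The protocol requires its collection. The TEAE rule includes it in the tables. The cut-off, read literally, excludes it. Neither sentence refers to the other.

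**Step 4. Effect on incidence.** SAP 5.6.2 counts subjects, so the table changes only if the dropped SAE was that subject's only one. With 6 to 12 subjects per initial dose group (SAP 4):

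- n = 12: 1/12 = 8.3 percentage points
- n = 6: 1/6 = 16.7 percentage points

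**Step 5. After the change.** If AEs are cut at Day 30 from the last dose, SAE collection and analysis both cover 0 to 30 days, and the gap is 0 for any *d*.

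**The case against.** The best defence is that the cut-off was never meant for AEs. Its paragraph concerns scheduled tests, time windows and by-visit tables, while the TEAE rule is the specific rule for AEs. The sentence also describes the assessment as scheduled for Day 30. If that means a nominal Day 30 limit, the two rules agree and no SAE in the window is lost. SAP 5.6.2 would list every SAE, which in groups of 6 to 12 leaves little room for one to go unseen. The safety analysis is descriptive, and the tolerability decision rests on Cycle 1 DLTs and toxicity up to Cycle 2. SAP section 8 also lets the sponsor settle data handling before database lock.

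Much of this stands, and it limits the point to a conflict in the text. It does not remove the conflict. The sentence covers data without qualification and turns on the assessment itself. A nominal Day 30 reading creates another problem: the visit window runs to Day 37 (30 + 7), so measurements from an on-time visit on Day 31 to 37 would be discarded. Leaving the choice until before lock, in an open-label study, means deciding on an SAE after it is known.

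Three stronger readings are tempting, and the documents do not support them:

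- **That these SAEs are collected and then excluded as a settled outcome.** The TEAE rule and the listings would include them.
- **That ending non-serious AE collection at an early last visit is a further defect.** That is a protocol choice about collection, and a coherent one, since later events may reflect the next therapy. The sentence "All AEs must be followed until resolution or for 30 days after the subject's last dose, whichever comes first" governs how long AEs are followed, not how long new ones are gathered.
- **That late related SAEs are lost.** The rule that they "should be reported to the sponsor regardless of the length of time that has passed since study completion" is a reporting duty. Events after Day 30 lie outside the TEAE window by design, and SAP 5.6.2 provides for listing all SAEs.

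**Conclusion.** The point holds as an unresolved contradiction within SAP 8.1, confined to subjects whose off-treatment visit is brought forward. For SAEs between that visit and Day 30, the plan both includes and excludes, with no order of precedence. On the literal cut-off they would drop out of the summary tables of a primary endpoint while remaining in the listings.

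The number of early visits, and of SAEs after them, is unknown. The 8.3 to 16.7 percentage points therefore show what one subject would do, not an expected bias, and assume that the subject had no other SAE. PFS and DOR are little affected, because SAP Tables 2 and 3 already censor at new anticancer treatment. The matter goes beyond missing detail because a stated rule, followed as written, would give the wrong table.

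**What to change.** Amend the cut-off sentence in SAP 8.1 before database lock so that it does two things:

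1. It applies only to visit-based measurements (such as laboratory values, vital signs and ECG), which are used through the actual off-treatment visit, including its +7-day window.
2. It states that AEs, SAEs and deaths with onset up to 30 days after the last dose are analysed under the TEAE rule whatever the date of the follow-up visit, with a flag on those that start after new anticancer therapy.

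The cost is one amended SAP passage and one derived flag. No change to AE collection in the protocol is needed. The small downside is that some included events may be confounded by the next therapy; the flag lets the reader see which.
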